#### Secondary endpoints in Part C:

Secondary endpoints assessed in Part C (through week 52) will be summarized with descriptive statistics for Part C SAF patients who entered Part C from Part B by the treatment groups received in Part C, as well as based on the treatment assignment in Part B (as randomized). Descriptive statistics will include number of patients, mean, median, Q1, Q3, standard deviation, minimum, and maximum for continuous efficacy variables; and patient counts and proportions for categorical efficacy variables. No formal statistical hypothesis testing will be performed. Inferential statistics will only be provided as needed.

All observed values, regardless of whether rescue treatment is used or data are collected after withdrawal from study treatment, will be used for analysis. No missing values will be imputed.

For categorical efficacy variables, the proportion of patients meeting response criteria at each visit will be calculated using the number of patients with non-missing value at the visit as the denominator.

For efficacy variables whose calculations involve baseline values, e.g., absolute (or percent) change from baseline, separate summaries will be provided for analyses using the study baseline and Part C baseline values. The study baseline is the latest available valid measurement taken prior to or on the date of the first dose of study drug administration (scheduled to be administered at the baseline visit [visit 3]). Part C baseline is the last available valid measurement taken prior to or on the date of the first dose of extended active treatment (scheduled to be administered at week 24 visit [visit 11]). For DSQ, Part C baseline; is defined in section 6.4; if it is missing, the latest available DSQ score prior to first Part C injection will be Part C baseline.

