If medically necessary, rescue medications (systemic and/or swallowed topical corticosteroids) or emergency esophageal dilation are allowed in study patients in Parts A, B and C. An endoscopy with biopsies will be performed prior to the initiation of rescue therapy unless COVID-19 restrictions prohibit this procedure. If the endoscopy with biopsies cannot occur due to COVID-19 restrictions, rescue treatment should not be delayed, and these patients will be eligible for Part C. Part C treatment will be initiated per the schedule of events and only at an in-clinic visit. Patients receiving rescue therapy may continue to receive study drug. They will remain blinded and will be asked to return to the clinic for all remaining study treatment visits and participate in all study assessments according to the schedule of events. However, they will not undergo any scheduled endoscopy/biopsies subsequent to the date of rescue.

Study Duration	The duration of the study for a patient (excluding the screening period) is approximately 64 weeks. This includes participation in the double-blind and extended active treatment part, and the follow-up period. For patients not entering Part C, the duration of the study is approximately 36 weeks.
-----------------------	--

End of Study Definition	The end of study is defined as the last visit of the last patient in the study.
--------------------------------	---

Population

Sample Size:	Part A: Approximately 80 patients (40 per treatment group). Patients may be adults ≥ 18 years of age or adolescents ≥ 12 and < 18 years of age. Part B: Approximately 210 patients (70 in each treatment group).
---------------------	---

Target Population:	The target population includes adult males and females ≥ 18 years of age and adolescent males and females ≥ 12 to < 18 years of age at the time of study entry with EoE. At least 10% of patients enrolled in Part B will be adolescents ≥ 12 to < 18 years of age. At least 30% of patients enrolled in Part B must have a history of prior use of swallowed topical corticosteroids.
---------------------------	---

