7.3. Rescue Treatments

If medically necessary (eg, for treatment of intolerable EoE symptoms), rescue medications (systemic and/or swallowed topical corticosteroids) or emergency esophageal dilation are allowed for study patients in Parts A, B, and C. An endoscopy with biopsy will be performed prior to the initiation of rescue therapy. Patients who undergo an endoscopy with biopsy due to the initiation of rescue therapy will not undergo the scheduled end of treatment visit endoscopy/biopsy at weeks 24 and 52. Patients who receive rescue treatment during the double-blind period of the study will not be eligible for the extended active treatment period unless an endoscopy with biopsy is performed prior to the initiation of rescue treatment. However, if the endoscopy with biopsies cannot occur due to COVID-19 restrictions, rescue treatment should not be delayed, and these patients will be eligible for Part C. Part C treatment will be initiated per the schedule of events and only at an in-clinic visit.

Patients receiving rescue therapy may continue to receive study drug. They will remain blinded and will be asked to return to the clinic for all remaining study visits for the double-blind treatment period and the follow-up period, and participate in all assessments for these visits according to the schedule of events specified in [Table 1](#), [Table 2](#), and [Table 3](#), except for endoscopy/biopsy, as noted above. For the purpose of efficacy analyses, patients who receive rescue treatment during the study will be considered treatment failures.

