8. TNSS and RQLQ(S)+12 will be administered only to patients with a documented history of allergic rhinitis; ACQ-5 will be administered only to patients with a documented history of asthma, and POEM will be administered only to patients with a documented history of AD. TNSS, POEM, ACQ-5 and RQLQ(S)+12 will be completed via electronic questionnaire and at the indicated site visits. The questionnaires will be administered only to the subset of patients who fluently speak the language in which the questionnaire is presented (based on the availability of validated translations in participating countries). See [Section 8.2.2.7](#), [Section 8.2.2.8](#), [Section 8.2.2.9](#), and [Section 8.2.2.10](#).
9. EoE-EREFS should be completed by the investigator before biopsies for all patients are performed. For Part B enrolled patients, EoE-EREFS will be performed by both the investigators who perform the endoscopies as well as a centralized reading center who will provide EoE-EREFS analysis and scoring from endoscopy imaging. For all endoscopies, the investigators will assess minor esophageal features including mucosal inflammatory and remodeling features.

10. Endoscopy/EoE-EREFS/biopsy procedures should be performed after all other efficacy and safety assessments. The EndoFLIP procedure to measure esophageal distensibility may be performed during the esophagogastroscope procedures at selected North American sites in approximately 150 adult patients.

Note: All randomized patients found to have stomach and/or duodenal abnormalities at baseline will have follow-up stomach and/or duodenal biopsies at weeks 24 and 52.

a. For patients who receive rescue treatment, endoscopy/EoE-EREFS/biopsy procedures will be performed prior to initiation of rescue treatment. Patients undergoing endoscopy/biopsy prior to rescue will not undergo the scheduled endoscopy/biopsy at weeks 24 and 52.

11. At visits 11 and 12, vital signs (body temperature, blood pressure, respiratory rate, heart rate) should be taken predose and 30 minutes (± 10 minutes) post-dose. Only predose vital signs are required at subsequent visits.

12. For adolescents only

13. In case of a positive urine pregnancy test, the study treatment will be withheld and a serum pregnancy test to confirm the pregnancy should be performed as soon as possible. A confirmed pregnancy will lead to study drug discontinuation in all cases.

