- Major elective surgical procedures
- Esophageal dilation (may be used as rescue procedure)
- Initiation or change of food-elimination diet regimen

Patients may receive the prohibited medications/procedures listed above as needed during the follow-up period, with the exception of live (attenuated) vaccine, which should not be used within 3 months after the last dose of study drug. Investigators are advised to prescribe prohibited medications/procedures judiciously, only when they are absolutely required for the appropriate management of study patients.

Blinded adjudication of prohibited medications and procedures will be performed by the medical monitor before database locks with documented procedures.

Rescue treatments (including both medications and procedures): If medically necessary (eg, for treatment of intolerable EoE symptoms), rescue medications (systemic and/or swallowed topical corticosteroids) or emergency esophageal dilation are allowed for study patients in Part B and C. If possible, an endoscopy with biopsy will be performed prior to the initiation of rescue therapy. Patients who undergo an endoscopy with biopsy due to the initiation of rescue therapy will not undergo the scheduled end of treatment visit endoscopy/biopsy at weeks 24 and 52. Patients who receive rescue treatment in Part B will not be eligible for the Part C extended active treatment period unless an endoscopy with biopsy is performed prior to the initiation of rescue treatment. However, if the endoscopy with biopsies cannot occur due to COVID-19 restrictions, rescue treatment should not be delayed, and these patients will be eligible for Part C. Patients receiving rescue therapy may continue to receive study drug. They will remain blinded and will be asked to return to the clinic for all remaining study visits and participate in all assessments for these visits except for endoscopy/biopsy, as noted above.

Blinded adjudication of rescue treatments will be implemented before database locks by considering the type of medication or procedure, indication, timing, frequency and the potential

impact of the use of the medication or procedure. The rescue treatments will be adjudicated by the medical director (or medical monitor) with documented procedures.

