### 5.6.1. Analysis of Co-Primary Efficacy Variable(s)

#### Histologic response (binary endpoint)

The proportion of patients achieving a histologic response of peak esophageal intraepithelial eosinophil (eos) count (from all 3 regions) of  $\leq 6$  eos/hpf at week 24 will be analyzed using the Cochran-Mantel-Haenszel (CMH) test to assess the difference in the proportion of responders in the FAS adjusting for the randomization stratification factors (age group [ $\geq 18$  vs.  $\geq 12$  to  $< 18$  years of age] and use of PPI at randomization [yes vs. no]). Estimates of treatment difference and its 95% confidence interval will be presented.

Data may be collected after the patient discontinued treatment and will be included in the analyses.

To account for use of rescue treatment (see Section 0), patients will be considered as non-responder for all time points subsequent to the use of rescue treatment in the primary analysis.

If week 24 biopsy is performed after the date when the first dose of Part C study drug is administered, patients will be considered as non-responder in the analysis.

Due to COVID-19 restrictions, patients may postpone the week 24 visit until an in-clinic visit can be done for biopsy. Before the biopsy procedure could be performed, study drug would be shipped to patients directly to enable them to extend their current assigned dose regimen of study drug. The data from those delayed week 24 visits will be used in the primary analysis as long as the patients keep the extended dosing before biopsy. However, for patients in whom extended dosing due to COVID-19 is interrupted (i.e. 2 or more consecutive doses or 5 or more doses in total missing during extended dosing period), their week 24 biopsy data will be set to missing and then imputed using MI.

Missing data at week 24 will be handled according to the reason for missingness as follows:

- If the peak esophageal intraepithelial eosinophil count at week 24 is missing due to COVID-19 pandemic, the data will be imputed by multiple imputation (MI) using a random seed number of 6681774 for 10 times based on patients who have non-missing eosinophil counts at week 24. The MI will utilize the regression method with treatment group, randomization stratification, baseline eosinophil count, and week 24 eosinophil count included in the regression model. The imputed week 24 eosinophil counts will

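### Week-52 histologic response rates omit rescued patients who have no week-52 biopsy, although the protocol calls rescued patients treatment failures

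*SAP*

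**What the plan says.** **Week 52.** SAP 5.6.2 (secondary endpoints in Part C) summarizes Part C efficacy descriptively. On rescue and withdrawal it says: "All observed values, regardless of whether rescue treatment is used or data are collected after withdrawal from study treatment, will be used for analysis". On missing data: "No missing values will be imputed". Categorical endpoints are computed "using the number of patients with non-missing value at the visit as the denominator".

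**Biopsy after rescue.** SAP 4.3 and Protocol 7.3 say that patients biopsied because rescue is starting "will not undergo the scheduled end of treatment visit endoscopy/biopsy at weeks 24 and 52". The Part C footnotes in Protocol 8.1.1 repeat this: "Patients undergoing endoscopy/biopsy prior to rescue will not undergo the scheduled endoscopy/biopsy at weeks 24 and 52". The protocol synopsis is broader and says of rescued patients that "they will not undergo any scheduled endoscopy/biopsies subsequent to the date of rescue".

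**Status of rescued patients.** For efficacy analyses, Protocol 7.3 states that "patients who receive rescue treatment during the study will be considered treatment failures". The sentence is not limited to Parts A and B.

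**Week 24.** SAP 5.6.1 applies the failure rule to histologic response: "patients will be considered as non-responder for all time points subsequent to the use of rescue treatment in the primary analysis". Values missing for reasons unrelated to COVID-19 are also non-responses, and COVID-19 missing values are multiply imputed.

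**Declared changes.** SAP 1.2.3 lists one departure from the protocol, the removal of the per protocol set.

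**The concern.** The co-primary and secondary endpoints are repeated at week 52 as secondary endpoints (SAP 4.4.2), and efficacy up to 52 weeks is a primary objective of Part C. For histologic response, the two time points treat rescue in opposite ways. At week 24 a rescued patient is a failure and stays in the denominator. At week 52 the same patient usually has no biopsy and leaves both numerator and denominator.

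The week-52 rates will be read beside the week-24 rates as evidence of durability. Part of any apparent maintenance or rise could then come from the change in counting rule rather than from patients.

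**Working it through.** The plan states no week-52 response, rescue or missing rate, so there is no figure to reproduce. The check has three steps.

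**1. Who leaves the denominator**

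- SAP 6.4, Table 3: for histology in Part C the week-52 target is Part C day 197 and the window is days 2 to 218.
- SAP 6.4, general rules: an unscheduled visit more than 4 weeks from target is not mapped. 197 − 28 = 169, so a pre-rescue biopsy at an unscheduled visit on days 2 to 168 is not mapped. That is 167 days; 167/196 is about 85% of the 28-week period.
- A patient rescued in Part B after a pre-rescue biopsy may enter Part C (Protocol 6.2.3 and 7.3) but skips the week-52 biopsy. The Part B biopsy predates Part C and cannot fill the week-52 window.
- Early-termination biopsies are mapped, and the 4-week limit names only unscheduled visits. Patients who terminate early with a biopsy in the window therefore stay in.
- Rescued patients with a mapped value, for example a pre-rescue biopsy on day 169 or later, stay in. They count as responders if the count is low enough, because no rescue rule applies.

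**2. Direction for rescued patients without a mapped biopsy**

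Let r be observed responders, n_obs patients with a week-52 value, and k rescued patients without one.

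- SAP rate: r / n_obs
- Failure-rule rate: r / (n_obs + k)
- Gap: p_obs × k / (n_obs + k), where p_obs = r / n_obs

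The gap is positive whenever k ≥ 1 and r ≥ 1.

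**3. Size under assumed rates**

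Assumptions, none taken from a stated week-52 figure: observed rate 60% (close to the Part A week-24 rate of 59.5% in SAP 2.3), and 15% of patients due for week 52 unbiopsied in total. Per 100 patients due, n_obs = 85 and r = 0.60 × 85 = 51. Only rescued patients are counted as failures; other missing patients stay excluded.

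| Rescued, no biopsy | Other missing | Failure-rule rate | Gap (points) |
|---|---|---|---|
| 2 | 13 | 51/87 = 58.6% | 1.4 |
| 5 | 10 | 51/90 = 56.7% | 3.3 |
| 10 | 5 | 51/95 = 53.7% | 6.3 |

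The table covers only rescued patients without a value. Reclassifying rescued patients who are now counted as responders would lower the rate further.

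For the other missing patients the sign is open. Take the middle row and put all 100 patients in the denominator:

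- all 10 others fail: 51/100 = 51%
- the 10 respond at 60%: (51 + 6)/100 = 57%
- all 10 respond: (51 + 10)/100 = 61%, above the observed 60%

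**The case against.** **The rule excludes nobody for rescue.** A reader might infer that SAP 5.6.2 removes all rescued and missing patients from every week-52 responder rate. It does not. Observed values are kept regardless of rescue, diary and questionnaire data continue after rescue, and early-termination biopsies are mapped in. The loss arises through the absent biopsy and affects only biopsy-based responder endpoints. This stands and limits the point to those.

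**Protocol 7.3 is a general sentence.** It is not applied literally to the DSQ co-primary, where Protocol Table 4 handles rescue by a hypothetical strategy with multiple imputation. Protocol 10.4.3.2.2 asks only for descriptive Part C summaries and sets no failure rule. This is fair, but for histologic response Table 4 and SAP 5.6.1 both use the failure rule, so on this endpoint week 52 departs from the plan's own convention.

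**Part C is uncontrolled and descriptive.** There is no formal testing. Rescue use, Kaplan-Meier time to first rescue and discontinuations with reasons are reported separately (SAP 5.3 and 5.4). Week 24 uses all randomized patients and week 52 only those dosed in Part C, so the rates differ in population anyway. These facts lower the stakes. They disclose rescue but do not correct the responder rate.

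**An observed denominator has a practical use.** At the Part B lock some patients will not yet have reached week 52 (SAP 8). This also stands. Any fuller denominator should be patients due for week 52, not the whole Part C set.

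**Conclusion.** The point holds for the three biopsy-based week-52 responder endpoints. The SAP's observed-case rule conflicts with Protocol 7.3 and with its own week-24 rule, and SAP 1.2.3 does not declare it. Measured against the failure rule, the reported rate is biased upward whenever at least one rescued patient lacks a mapped biopsy and there is at least one responder.

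The size cannot be derived from the documents. Under the stated assumptions the gap is 1.4 to 6.3 points.

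A reader might go further and conclude that durability is overstated by 9 points, since 0.60 × (1 − 0.15) = 51%. The documents do not support that. The 15% in SAP 2.3 is a sample-size dropout assumption for Part B, not a week-52 missing-biopsy rate, and patients who terminate early may still have a mapped biopsy. The 9 points also require every missing patient to be a failure, whereas outside rescue the direction is unknown.

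**What to change.** In SAP 5.6.2, keep the observed-case rate for each week-52 histologic responder endpoint and add a second rate beside it:

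- **Denominator:** Part C SAF patients due for week 52 at the data cut.
- **Rescued on dupilumab:** non-responders, whether or not they have a mapped biopsy.
- **Rescued on placebo in Part B:** shown separately. Counting everyone rescued at any time would make such a patient a dupilumab failure before the first dupilumab dose.
- **Other missing values:** as in Part B, with non-COVID missing as non-responder and COVID-19 missing by multiple imputation or shown separately.
- **Numbers missing by reason:** given for each treatment sequence.

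If observed-case stays the main summary, list it in SAP 1.2.3 as a departure from Protocol 7.3.

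The cost is SAP wording, one extra table row per endpoint, and a somewhat lower week-52 rate on the added row. Endpoints that do not need a biopsy, and the schedule of biopsies after rescue, need no change for this purpose.

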6.2.3. Exclusion Criteria for Part C (the Extended Active Treatment Period)

A patient who meets any of the following criteria will not be permitted to enter Part C (the extended active treatment period):

1. Patients who, during the double-blind treatment period, developed a serious adverse event (SAE) and/or adverse event (AE) deemed related to study drug, which in the opinion of the investigator could indicate that continued treatment with study drug may present an unreasonable risk for the patient
2. Patients who, during the double-blind treatment period, were prematurely withdrawn because of a protocol violation, poor compliance, or inability to complete required study assessments
3. Patients who became pregnant during the double-blind treatment period
4. Patients who are prematurely discontinued from study drug due to an AE (patients who are prematurely discontinued from study drug due to lack of efficacy are eligible to enter Part C)
5. Patients who did not undergo endoscopy with biopsies prior to receiving rescue treatment
Note: If the endoscopy with biopsies cannot occur due to COVID-19 restrictions, rescue treatment should be initiated without delay and these patients will be eligible to participate in Part C when the patient can next return to the clinic.
6. Systemic hypersensitivity to dupilumab or the excipients of the drug product based on participation in Part A or Part B

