10.4.3.2.2. Analysis of Secondary Efficacy Endpoints in Part C

Efficacy variables measured in Part C will use the last non-missing value prior to the first dose of extended active treatment study drug as their baseline assessments. These efficacy variables will be summarized with descriptive statistics by received treatment in Part C. Inferential statistics will only be conducted as needed.

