10.5. Additional Statistical Data Handling Conventions

The following analysis and data conventions will be followed:

Definition of baseline:

- The baseline assessment for each study part will be the latest, valid predose assessment available for the corresponding study part, respectively

General rules for handling missing data:

- If the start date of an AE or concomitant medication is incomplete or missing, it will be assumed to have occurred on or after the intake of study medication, except if an incomplete date (eg, month and year) clearly indicates that the event started prior to treatment. If the partial date indicates the same month or year of the intake of study medication date, then the start date by the study medication intake date will be imputed; otherwise, the missing day or month by the first day or the first month will be imputed.
- No imputations for missing laboratory data, ECG data, vital sign data, or physical examination data will be made.

Unscheduled assessments:

- Extra assessments (laboratory data or vital signs associated with non-protocol clinical visits or obtained in the course of investigating or managing AEs) will be included in listings and summaries. If more than 1 laboratory value is available for a given visit, the first observation will be used in summaries and all observations will be presented in listings.

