### 6.1. Definition of Baseline for Efficacy/Safety Variables

Unless otherwise specified, the study baseline assessment for all measurements will be the latest available valid measurement taken prior to the first administration of study drug. If any randomized patients are not treated, the baseline will be the last value on or prior to the randomization. In addition, Part C baseline is defined as the last available valid measurement taken prior to the first dose of extended treatment in Part C. The baseline of DSQ is defined in Section 6.4.

The following rules specify the determination by both date/time information:

1. For AE, lab (including biomarker), PK and ADA data, both date and time of the measurement will be used to determine baseline by comparing with the first injection date and time.
2. For other data except AE, lab (including biomarker), PK or ADA, only date of the measurement will be used to determine baseline by comparing with the first injection date.

For re-screened patients, all data from the same patient will be used to derive baseline regardless of whether the data are from the screen failure subject ID or enrolled subject ID.

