**Part C (only applies to patients who received at least 1 dose of Part C study drug)**

**Table 3: Analysis Visit Window for Efficacy Endpoints in Part C**

Visit from SOE	Target Study Day in Part C a	Analysis Window based on Study Day in Part C	
		Histology endpoints, Transcriptome endpoints, EREFS, EndoFLIP endpoints	PRO endpoints
Baseline of Part C	1	≤1	≤1
Week 36	85		[2, 141]
Week 52 (Part C end of treatment)	197	[2, 218]	[142, 218]
Week 56 b (Extended period of Part C)	225		[219, 232]
Week 58 b (Extended period of Part C)	239		[233, 246]

Visit from SOE	Target Study Day in Part C a	Analysis Window based on Study Day in Part C	
		Histology endpoints, Transcriptome endpoints, EREFS, EndoFLIP endpoints	PRO endpoints
Week 60 b (Extended period of Part C)	253	[247, 260]	
Week 62 b (Extended period of Part C)	267	[261, 274]	
Week 64 b (Extended period of Part C)	281	>=275	

**Error! Reference source not found.** Study days are calculated from the day of 1st injection of Part C. Study day = (date of assessment – 1st injection date +1) when date of assessment ≥ 1st injection date; otherwise study day = (date of assessment – 1st injection date). If patient never received any dose of study drug, randomization date will be used in place of 1st injection date.

b Those are dummy analysis visits windows for patients with extended dosing in Part C. ET or unscheduled visit occurred after week 52 visit will be mapped per Table 5.

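### The Part C baseline for endoscopy and biopsy endpoints has no earliest date, so a patient with no usable on-study value before Part C is assigned the pre-treatment screening value

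*SAP*

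**What the plan says.** Three places define the Part C baseline, and none gives an earliest date:

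- SAP 5.6.2, on secondary endpoints in Part C: "Part C baseline is the last available valid measurement taken prior to or on the date of the first dose of extended active treatment".
- SAP 6.1: "Part C baseline is defined as the last available valid measurement taken prior to the first dose of extended treatment in Part C".
- Protocol 10.4.3.2.2: Part C efficacy variables "will use the last non-missing value prior to the first dose of extended active treatment study drug as their baseline assessments".

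SAP Table 3 has a row headed "Baseline of Part C" that accepts any Part C study day up to and including day 1, with no lower limit. It covers histology, transcriptome, EREFS and EndoFLIP endpoints.

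The general convention in Protocol 10.5 is narrower: "The baseline assessment for each study part will be the latest, valid predose assessment available for the corresponding study part, respectively". The SAP does not repeat it. SAP 1.2.3, which lists departures from the protocol's statistical section, names only the removal of the per-protocol set.

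For variables that involve a baseline, SAP 5.6.2 asks for separate Part C summaries from the study baseline and from the Part C baseline. They use all observed values, without imputation and without formal tests.

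**The concern.** The summary from the Part C baseline is there to isolate what happens after week 24: whether response is kept in patients continuing on dupilumab, and how former placebo patients respond. It does so only if the baseline describes the patient at Part C entry. If the rule reaches back to screening, a patient's two summaries are identical and the Part C figure contains the Part B effect. A stable patient then looks newly improved, and a patient who is losing response can look improved. In effect a pre-treatment value is carried forward, although SAP 5.6.2 says that nothing is imputed in Part C.

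The week-52 versions of the endpoints are named as secondary endpoints (SAP 4.4.2), and Part C has its own efficacy objective (SAP 1.2.1).

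**Working it through.** **1. Which measurements can serve as Part C baseline.** Under Protocol 8.2.2.1 and the schedule of events, endoscopy and biopsy before Part C take place at screening (visit 2) and week 24 (visit 11), plus a pre-rescue or early-termination procedure where one occurs. If no value after the first Part B dose is usable, the last available one is from visit 2, before any study drug.

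**2. How that can happen.**

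- The week-24 biopsy comes after the first Part C dose. The SAP foresees this: "If week 24 biopsy is performed after the date when the first dose of Part C study drug is administered", SAP 5.6.1 counts the patient as a non-responder, and SAP 5.6.2 sets the continuous endpoints to missing. Both rules serve Part B. No rule covers the Part C baseline.
- The week-24 value is missing because of COVID-19, a case that SAP 5.6.1 handles for Part B only.
- A specimen is lost or unreadable, or an EREFS video cannot be read centrally. SAP 4.4.2 moves the whole analysis to investigator scores if, for example, more than 20% of the FAS lack a central reading. Below that it states no patient-level substitute, although Protocol 10.4.3.2.1 does.

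In each case the patient must also have no pre-rescue or early-termination value, and must have a week-52 value.

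**3. Error for one patient.** Let S be the screening value, W the value at Part C entry that is not available, and V the week-52 value.

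Reported Part C change = V − S = (V − W) + (W − S).

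The error is W − S, the patient's Part B change. The documents give no patient values, so these peak counts (eos/hpf) are assumed:

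| S | W | V | True Part C change | Reported Part C change | Error |
|---|---|---|---|---|---|
| 80 | 5 | 5 | 0 (0%) | −75 (−93.75%) | −75 |
| 80 | 5 | 30 | +25 (+500%) | −50 (−62.5%) | −75 |
| 80 | 80 | 5 | −75 (−93.75%) | −75 (−93.75%) | 0 |

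The second row reverses the sign. The third, a former placebo patient unchanged in Part B, shows no error.

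**4. Error for an arm.** If k of n patients are affected, the mean absolute change shifts by (k/n) × their mean Part B change. Take n = 70 for a continuing arm (the planned Part B size) and n = 70/2 = 35 for each re-randomised placebo arm, assuming that all enter Part C and have week-52 data. The documents do not give k; 1 to 7 is an assumed range.

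| k | n = 70 | n = 35 |
|---|---|---|
| 1 | 1.4% | 2.9% |
| 3 | 4.3% | 8.6% |
| 7 | 10% | 20% |

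Each entry is a share of the affected patients' mean Part B change. In the placebo arms that change may be small, so the larger share need not mean a larger error.

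For percent change, the listed eosinophil endpoint, the first pattern gives −93.75/70 = −1.3 percentage points per affected patient and 7 × (−93.75)/70 = −9.4 points for seven.

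**The case against.** **The routes are exceptions.** The Part C schedule footnotes (Protocol 8.1.1.2) require the week-24 endoscopy with biopsy before Part C dosing, and COVID-19 extended dosing keeps patients on their Part B regimen until it is done. This stands, and it is why the number is probably small. The SAP nevertheless writes rules for the exceptions in Part B and none for the Part C baseline.

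**Many patients without a standard week-24 value do not fall back.** A pre-rescue or early-termination biopsy is used first. A biopsy set to missing in Part B for interrupted extended dosing is still an observed value before Part C. This also stands.

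**The COVID-19 rescue provision might be read as a route by itself.** For patients who could not be biopsied before rescue, Protocol 6.2.3 says "rescue treatment should be initiated without delay and these patients will be eligible to participate in Part C". That alone does not produce the error. On the synopsis wording, rescued patients have no later scheduled endoscopy, so no scheduled week-52 value exists from which to compute a change. On Protocol 7.3 and SAP 4.3, only patients biopsied because of rescue skip week 24; the others are still due a week-24 biopsy, which counts because Part C uses values regardless of rescue.

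**Protocol 10.5 might be thought to settle it**, since visit 2 belongs to the Part A and B schedule. But Protocol 10.4.3.2.2 and SAP 5.6.2 and 6.1 are more specific and contain no such limit.

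**Table 3 is weak support.** SAP 6.4 applies the windows when scheduled-visit data are unavailable, and visit 2 is a scheduled visit. The defect rests on the definitions; the table merely fails to prevent it.

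**The effect on summaries is modest.** Medians and quartiles are also given, responder proportions need no baseline, and percent change from a low baseline is noisy anyway: one patient going from 5 to 10 adds 100/70 = 1.4 points to a 70-patient mean. All of this stands.

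**Conclusion.** The rule gives a wrong Part C change for a narrow group: patients who enter Part C with no usable endoscopy or biopsy value after the first Part B dose and on or before the first Part C dose, and who have a week-52 value. For each of them the error is the full Part B change and can show loss of response as improvement. For an arm it is the affected share of that change: 1.4% per patient at n = 70 and 2.9% at n = 35, under the assumption of full entry and complete week-52 data. The number affected is unknown. Only the descriptive change summaries from the Part C baseline are touched; the study-baseline summaries, responder proportions, hypothesis tests and primary results are not.

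Two stronger conclusions are tempting:

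- A reader might infer that the comparison of QW with Q2W durability is distorted. That would need unequal numbers or unequal Part B changes in the two arms. The documents show neither, and they plan no such test.
- A reader might infer from SAP 6.1 that almost every patient falls back to screening. It requires a measurement before the first Part C dose and compares dates only for endoscopy data, while the week-24 biopsy and the first Part C dose belong to the same visit. But SAP 5.6.2, which is specific to Part C efficacy, includes the dose date, and Table 3 includes day 1. The two sections need aligning; they do not support that reading.

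**What to change.** In SAP 5.6.2 and 6.1, define the Part C baseline for peak eosinophil count, EREFS, EoEHSS, transcriptome and EndoFLIP endpoints as the last valid measurement after the first Part B dose and on or before the date of the first Part C dose. If there is none, set it to missing, leave the patient out of the change summary from the Part C baseline only, keep the patient in the study-baseline summary, and report the number excluded by arm. Add the same lower limit to the baseline row of Table 3 for consistency.

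In the same edit, align SAP 6.1 with 5.6.2 on measurements taken on the dosing date, and reconcile both with Protocol 10.5.

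The cost is a few sentences and one programming condition. A few patients drop out of one descriptive summary. No patient procedure, alpha allocation or primary analysis changes.
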